### 6.1 Definitions

#### 6.1.1 Adverse Event

An AE is any untoward medical occurrence in a patient administered a study drug which may or may not have a causal relationship with the study drug. Therefore, an AE is any unfavorable and unintended sign (including abnormal laboratory finding), symptom, or disease which is temporally associated with the use of a study drug, whether or not considered related to the study drug.

An AE also includes any worsening (i.e. any clinically significant change in frequency and/or intensity) of a pre-existing condition that is temporally associated with the use of the study drug.

#### 6.1.2 Serious Adverse Event

A SAE is any untoward medical occurrence that at any dose:

- Results in **death** – includes all deaths, even those that appear to be completely unrelated to study drug (e.g. a car accident in which a patient is a passenger).
- Is **life-threatening** – in the view of the investigator, the patient is at immediate risk of death at the time of the event. This does not include an AE that had it occurred in a more severe form, might have caused death.
- Requires in-patient **hospitalization** or prolongation of existing hospitalization. In-patient hospitalization is defined as admission to a hospital or an emergency room for longer than 24 hours. Prolongation of existing hospitalization is defined as a hospital stay that is longer than was originally anticipated for the event, or is prolonged due to the development of a new AE as determined by the investigator or treating physician.
- Results in persistent or significant **disability/incapacity** (substantial disruption of one's ability to conduct normal life functions).
- Is a **congenital anomaly/birth defect**

- Is an **important medical event** – Important medical events may not be immediately life-threatening or result in death or hospitalization, but may jeopardize the patient or may require intervention to prevent 1 of the other serious outcomes listed above (e.g., intensive treatment in an emergency room or at home for allergic bronchospasm; blood dyscrasias or convulsions that do not result in hospitalization; or development of drug dependency or drug abuse). Any malignancy (other than basal cell skin cancers) would be considered a medically important event.

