## 1. INTRODUCTION AND RATIONALE

Corticosteroids are routinely prescribed for the post-operative management of inflammation and pain following retinal surgery. Persistent ocular inflammation can increase the risk of ocular complications such as increased intraocular pressure (IOP), ocular pain, and reduced visual outcomes, where as untreated pain can affect overall patient satisfaction. Despite the widespread use of topical eyedrops, this means of treatment is often associated with poor patient compliance. This issue is further complicated in pediatric patients, who often dislike eye drops leading to difficulty with administration in the post-op period by parents. Largely across preparations, there is poor bioavailability from eyedrops with less than 5% of the applied dose of topical preparations predicated to reach the intraocular tissues.

To optimize the delivery of a corticosteroid after ocular surgery, a sustained-release intracanalicular dexamethasone insert (DEXTENZA, Ocular Therapeutix, Inc) has been approved by the FDA to treat ocular pain and to control inflammation after ocular surgery.

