#### **Visit 2 Surgical Visit ( Day 0)**

- Subject reported AE's prior to surgery
- Indicate the incision type, location, and size (mm)
- Punctum examination
- If you are a patient who could possibly be pregnant (you have started menstruation), a urine pregnancy test will be performed, and it must be negative in order to continue in the study.
- Randomization and potential placement of intracanalicular dexamethasone insert if assigned to treatment arm
- Record any surgical complications

**Visit 3 (Day 1 +/- 3 days) Visit 4 (Day 7 +/- 3 days) Visit 5 (Day 28 +/- 3 days)  
Visit 6 (Day 45 +/- 3 days)**

- Subject reported AE's after surgery
- Document administration of prescribed medication (if used and number of drops used)
- Ocular Pain Assessment (FLACC)
- Distance VA testing, when applicable
- Best-corrected visual acuity as measured by ETDRS or HOTV chart at 4m based on patient age (HOTV for pre-literate patients)
- Anterior chamber cell count
- Anterior chamber cell flare
- Punctum examination and ease of insert visualization (for patients receiving DEXTENZA insert only)
- Intraocular pressure
- Ophthalmic Examination including dilated fundus exam
- Satisfaction Survey (at the end of visit 6 only)

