## 6. SAFETY DEFINITIONS, REPORTING, AND MONITORING

Safety will be assessed from surgery through 45 days post surgery. Safety will be assessed only by frequency and incidence of events of special interest (ESI) and SAEs.

Monitoring for ESIs and SAEs will occur from the initial study-specific procedure through 28 days post last study drug dose (including the weaning doses).

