### 6.1.3 Events of Special Interest

The patients enrolled in this trial will have trauma to the eye as a direct result of surgery with known and previously reported potential significant eye-related events. The following events will not be included in the primary safety outcome, but they are clinical events of special interest (ESI) that may relate to safety and that will be tracked and reported in the trial results. These AEs are to be reported to study database, regardless of whether these events meet serious criteria or unexpectedness:

- Elevated intraocular pressure
- Eye pain and local erythema
- Infection
- Allergic reaction
- Trauma to the punctum
- Eyelid swelling
- Hazy or cloudy vision
- Feeling like something is in the eye
- Increased sensitivity to light

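### Section 6 limits safety to SAEs and nine listed events, none of them a retinal, lens or measured vision-loss event, while the endpoints and section 5.2.3 cover all AEs

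*Combined protocol and SAP*

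**What the plan says.** **Narrow scope.** The opening of section 6 says: "Safety will be assessed only by frequency and incidence of events of special interest (ESI) and SAEs". Section 6.2 names ESIs and SAEs, and nothing else, for entry in the study database. Section 8.1.2 promises a general summary of safety reports, but specifies a presentation only for SAEs and ESIs.

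**Wide scope.** The synopsis and section 2.2 list the frequency and severity of AEs up to day 45 as a secondary endpoint. Section 5.2.3 has the investigator record every AE. Section 6.1.1 defines an AE broadly, including worsening of an existing condition.

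**The ESI list.** Section 6.1.3 says of its nine events: "These AEs are to be reported to study database, regardless of whether these events meet serious criteria or unexpectedness". They cover pressure, pain and redness, infection, allergy, punctal trauma, lid swelling and three visual or sensory complaints. The nearest to vision loss is "Hazy or cloudy vision".

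**The SAE definition.** Section 6.1.2 has six criteria. For hospitalisation: "In-patient hospitalization is defined as admission to a hospital or an emergency room for longer than 24 hours". Disability is explained as "substantial disruption of one's ability to conduct normal life functions". An important medical event is one that "may jeopardize the patient or may require intervention to prevent 1 of the other serious outcomes listed above".

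**What is measured.** Section 5.2.1 and Tables 1 and 2 schedule BCVA and "Ophthalmic Examination including dilated fundus exam" in both arms at screening and at all four post-operative visits. BCVA is an endpoint as mean change.

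**The concern.** Section 4.1.1 enrols children for detachment repair, vitrectomy, laser and cryotherapy. The serious ocular events one would look for after these procedures are retinal, vitreous or lens events and loss of vision. Section 1 itself says: "Persistent ocular inflammation can increase the risk of ocular complications such as increased intraocular pressure (IOP), ocular pain, and reduced visual outcomes". Of those three consequences, pressure and pain are ESIs; measured visual loss is not.

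Two things are at stake. First, two teams could build different safety databases from this protocol, one holding all AEs and one holding only ESIs and SAEs, and both could cite the text. Second, under the narrow reading, a child with a re-detachment or a large acuity fall could be missing from the safety tables unless someone classified the event as serious. Safety is a stated objective and the arms are small, so one event matters.

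**Working it through.** **1. Design figures.** Section 4.1 gives two procedure groups of 10 insert and 5 control children: 2 × (10 + 5) = 30, the stated sample size, with 20 insert and 10 control. Section 8.1 calls this a feasibility study without power to compare arms, so there is no power figure to reproduce.

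**2. Tracing one event.** Take a recurrent detachment repaired as a day case.

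| Route | Does it force capture? |
|---|---|
| ESI list (6.1.3) | No retinal term. Hazy vision may apply, but is not tied to measured acuity |
| SAE: hospitalisation (6.1.2) | Not met at 24 hours or less |
| SAE: disability (6.1.2) | Possible; no acuity threshold |
| SAE: important medical event (6.1.2) | Possible whatever the length of stay; no ocular example, so a judgement |
| AE recording (5.2.3) and AE secondary endpoint (2.2) | Yes, but section 6 restricts the safety assessment, 6.2 does not name such AEs for the database, and 8.1.2 specifies no all-AE table |

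Section 3.1 makes the trial open-label. Masked assessment is stated only for FLACC (Appendix 10.3).

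**3. Can mean BCVA stand in?** Shift in arm mean = one child's loss ÷ number in the arm. The documents give no loss to use; I assume 0.3 logMAR (3 lines at 0.1 per line).

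- All insert children: 0.3 / 20 = 0.015
- All controls: 0.3 / 10 = 0.03
- Within a procedure group, insert: 0.3 / 10 = 0.03
- Within a procedure group, control: 0.3 / 5 = 0.06

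At an assumed 0.6 logMAR each figure doubles: 0.03, 0.06, 0.06 and 0.12. The SD, minimum and maximum planned in section 8.1 would hint at an extreme value, but do not say how many children lost vision.

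**4. Effect of one uncounted event** (exact Clopper-Pearson 95% intervals).

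| Arm | Counted | Missed |
|---|---|---|
| Insert | 1/20 = 5.0% (0.1% to 24.9%) | 0/20 = 0% (0% to 16.8%) |
| Control | 1/10 = 10.0% (0.3% to 44.5%) | 0/10 = 0% (0% to 30.8%) |

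**5. Chance that the insert arm shows at least one event.** With event rate p and capture probability c, this is 1 − (1 − pc)^20. Neither p nor c is in the documents; all values are assumptions.

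| p | c = 1 | c = 0.5 |
|---|---|---|
| 5% | 64.2% | 39.7% |
| 10% | 87.8% | 64.2% |
| 20% | 98.8% | 87.8% |

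**The case against.** The strongest reply is that the protocol already covers these events. A re-detachment is plainly an AE under section 6.1.1, every AE is recorded under 5.2.3, and AEs are a secondary endpoint. Vision is measured at every follow-up visit, and section 4.1.2 excludes children who cannot do acuity testing. The choice of ESIs is a judgement, and this is a descriptive feasibility study. All of that stands, and it means that findings at the dilated examination can enter an endpoint, as AEs. It does not settle the matter, because section 6 says only ESIs and SAEs count towards safety, and 6.2 and 8.1.2 follow that restriction. The reply relies on one half of a contradiction.

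A reader might also infer that the 24-hour rule keeps day-case re-operations out of the safety result. The text does not support that. Hospitalisation is one of six criteria; an important medical event needs no admission, and its examples are illustrations, not limits. A re-operation to prevent lasting visual loss fits that wording.

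A reader might further infer that events will be counted differently by arm. Open-label judgement makes this possible, but nothing in the documents shows that it would happen, or that these complications would differ between insert and drops.

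**Conclusion.** The point holds as a contradiction over AE scope, combined with an ESI list and a BCVA summary that do not force capture of visual harm. It should be corrected, but it is not a fatal flaw. Under the narrow reading in section 6, a re-detachment or large acuity loss in one child enters the safety result only if it is picked up as hazy vision or meets an SAE criterion; for a child not admitted beyond 24 hours, the SAE route rests mainly on judging the event disabling or medically important. Omission is a possibility, not a consequence of the definitions. One missed event would turn 5.0% into 0% in the insert arm or 10.0% into 0% in the control arm. An assumed 0.3 logMAR loss in one child would move the arm means by only 0.015 and 0.03. The arm sizes are the protocol's; the size of the loss, the event rates and the capture rates are my assumptions.

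**What to change.** 1. Reconcile sections 6, 6.2 and 8.1.2 with the synopsis, 2.2 and 5.2.3, so that all AEs are entered in the database and tabulated by arm with severity.
2. Add to the section 6.1.3 list, for both arms: new or recurrent retinal detachment, vitreous haemorrhage or lens opacity found at the scheduled dilated examination, and any unplanned repeat procedure on the study eye.
3. Beside mean BCVA change, report by arm the number of children who lost 3 or more lines from screening on the same chart type. Lines suit both charts, because Appendix 10.2 scores HOTV by line. Show the counts by visit, with days 28 and 45 as the main time points, so that expected early post-operative falls are not mixed in.

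The 24-hour wording need not change. An ocular example under important medical event would be an optional clarification.

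The cost is a wording amendment, a few extra fields for an examination already done, one derived variable and an all-AE table. The fundus findings and repeat procedures would still be recorded by unmasked staff, but against named terms. Some expected disease-related events will be listed and must be read against the control arm.

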### 6.1.3 Events of Special Interest

The patients enrolled in this trial will have trauma to the eye as a direct result of surgery with known and previously reported potential significant eye-related events. The following events will not be included in the primary safety outcome, but they are clinical events of special interest (ESI) that may relate to safety and that will be tracked and reported in the trial results. These AEs are to be reported to study database, regardless of whether these events meet serious criteria or unexpectedness:

- Elevated intraocular pressure
- Eye pain and local erythema
- Infection
- Allergic reaction
- Trauma to the punctum
- Eyelid swelling
- Hazy or cloudy vision
- Feeling like something is in the eye
- Increased sensitivity to light

## 6.2 Recording and Reporting Adverse Events

All ESIs and SAEs will be recorded in the study database.

All SAEs, regardless of assessment of causal relationship to study insert will be reported to the sponsor. The sponsor will provide these reports to Ocular Therapeutix.

The investigator will promptly report to the IRB all unanticipated problems involving risks to patients. This includes death from any cause and all SAEs

related to the use of the study insert. All SAEs will be reported to the IRB, regardless of assessed causality.

## **7. STUDY VARIABLES**

### **7.1 Demographic and Baseline Characteristics**

Baseline characteristics will include standard demography (e.g. age, race, weight, height, etc.), disease characteristics including medical history, and medication history for each patient.

## **8. STATISTICAL CONSIDERATIONS**

### **8.1 Sample Size Considerations and Analysis Plan**

This is a feasibility study and the sample size of 30 is not designed to provide power to determine any differences between arms.

Analysis results will be presented by study drug vs. standard of care topical drops overall and by surgical procedure group.

Descriptive statistics such as number of observations, mean, median, standard deviation, minimum and maximum will be presented by treatment arms for continuous variables (such as age, weight, etc.). Other descriptive statistics such as counts, proportions, and/or percentages will be presented by group to summarize discrete variables (such as race, sex, etc.).

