**Clinical Study Protocol Synopsis**

Title	The Evalua T ion of the Safety and E fficacy of Sustai N ed Release D examethasone Intra c analicular In s ert (DEXTENZA) in p E diatric patients following R etinal surgery or laser treatment under anesthesia
Site Location(s)	Duke University Eye Center
Principal Investigator	[name]
Objective(s)	To determine safety and efficacy of the dexamethasone ophthalmic insert in pediatric patients following retinal surgery or laser treatment under anesthesia
Study Design	Prospective Open-label Interventional Study
Study Duration	45 days postoperative
Estimated Study Completion Date	August 1, 2023
Population	
Sample Size:	30
Target Population:	Pediatric patients ages 3 to 17 undergoing routine retinal surgeries or laser treatment under anesthesia
Study Drug	DEXTENA (dexamethasone ophthalmic insert) 0.4 mg, for intracanalicular use
Dose/Route/Schedule:	
All eyes will undergo routine retinal surgery or laser treatment under anesthesia.
 
Patients in each treatment group (surgery or laser) will be randomized 2:1 at the time of surgery/laser to either:
 
 
1) Treatment Arm: Dextenza insert intraoperatively for perioperative ocular inflammation and pain. These patients will not be prescribed topical
 

steroid drops post-operatively, or

- 2) Control Arm: Prednisolone forte 1% steroid drop taper for 28 days post-operatively to treat perioperative ocular inflammation and pain; drops four times per day (QID) on days 0-7, three times per day (TID) on days 7-14, twice per day (BID) on days 14-21 and once per day (QD) on days 21-28.

Each treatment group (surgery or laser) will include 15 patients total, 10 receiving Dextenza and 5 receiving the control drug.

Drops for dilation and antibiotic coverage will be used as clinically indicated in all groups and arms.

There will be a total of six visits for both treatment arms Screening/Baseline visit (day -30 to 0), Surgical Visit (day 0), and four post-operative follow up appointments occurring at post-op day 1, 7, 28/30 and 45 ( +/- three days for all post-operative timepoints). Exams to be performed on these days are outlined in section 5.1.. Treatment Arm Schedule of Events in Table 1. Control Arm Schedule of Events in Table 2

---

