## 2. STUDY OBJECTIVES

### 2.1 Primary Objective

To determine if pediatric retinal patients would benefit from the placement of the 0.4 mg sustained release Dexamethasone intracanalicular insert (DEXTENZA) in the inferonasal lacrimal system during surgery in the surgical/treated eye compared to topical ocular drop therapy to manage post-operative pain (measured with Face, Legs, Activity, Cry Consolability (FLACC) Behavioral Pain Rating Scale). Pain will be measured at each visit with final outcome determined by the FLACC Behavioral Pain Rating Scalescore on day 45.

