### **4. SELECTION, WITHDRAWAL, AND REPLACEMENT OF PATIENTS**

#### **4.1 Study Population**

The study aims to enroll 30 pediatric patients undergoing routine retinal surgery or laser treatment under anesthesia. Patients in each treatment group (surgery or laser) will be randomized 2:1 at the time of surgery/laser to receive either:

- 3) Treatment Arm: Dextenza insert intraoperatively for perioperative ocular inflammation and pain. These patients will not be prescribed topical steroid drops post-operatively, or
- 4) Control Arm: Prednisolone forte 1% steroid drop taper for 28 days post-operatively to treat perioperative ocular inflammation and pain; drops four times per day (QID) on days 0-7, three times per day (TID) on days 7-14, twice per day (BID) on days 14-21 and once per day (QD) on days 21-28.

Each treatment group (surgery or laser) will include 15 patients total, 10 receiving Dextenza and 5 receiving the control drug. Drops for dilation and antibiotic coverage will be used as clinically indicated in all groups throughout the study period. Follow up will occur at post-op day 1, 7, 28/30 and 45 (+/- three days for all post-operative timepoints).

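### The objectives promise to determine benefit over drops, but section 8.1 disclaims power for any difference and plans only summaries by arm, with no between-arm estimate or interval

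*Combined protocol and SAP*

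**What the plan says.** The synopsis gives the objective as "To determine safety and efficacy of the dexamethasone ophthalmic insert in pediatric patients following retinal surgery or laser treatment under anesthesia". Section 2.1 makes it comparative: "To determine if pediatric retinal patients would benefit from the placement of the 0.4 mg sustained release Dexamethasone intracanalicular insert", "compared to topical ocular drop therapy to manage post-operative pain", with the "final outcome determined by the FLACC Behavioral Pain Rating Scalescore on day 45". The primary endpoint in the synopsis poses the same comparison, using evaluate in place of determine.

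Section 4.1 sets the design: "The study aims to enroll 30 pediatric patients undergoing routine retinal surgery or laser treatment under anesthesia", and "Patients in each treatment group (surgery or laser) will be randomized 2:1 at the time of surgery/laser to receive either" the insert or the drops. Each procedure group is to have 15 children, 10 on the insert and 5 on drops.

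Section 8.1 then states "This is a feasibility study and the sample size of 30 is not designed to provide power to determine any differences between arms". On analysis it says "Analysis results will be presented by study drug vs. standard of care topical drops overall and by surgical procedure group", and lists the usual descriptive statistics, with demographic variables as the examples. Sections 8.1.1 and 8.1.2 cover disposition, exposure, safety summaries and medications. Section 8.1.2 presents serious adverse events and events of special interest overall and states no split by arm. Any split there rests on the general sentence in 8.1.

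**The concern.** The objectives ask a comparative question that the analysis section does not answer. Section 8 names no between-arm difference, confidence interval or model, and no estimator that uses the randomisation groups. It does not mention FLACC. It calls the trial a feasibility study, yet neither the endpoints nor sections 2.1 and 2.2 contain a feasibility objective or criterion.

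Followed as written, the plan produces two columns of means and percentages, from 20 and 10 children. If the columns look alike, nothing in the report tells the reader how far apart the true values could be. If they look different, nothing says how much of that is chance. The list of statistics is introduced as examples, so a contrast could be added later, but in an open-label trial its form would then be chosen with the data in view.

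**Working it through.** **Inputs.** Section 4.1 gives two procedure groups of 10 insert and 5 drops: 2 × (10 + 5) = 30, or 20 v 10, which agrees with the stated total. Section 8.1 gives no significance level, effect size, SD or power, so there is no calculation of the plan's own to reproduce. My assumptions are two-sided 95% intervals and all 30 children evaluable (best case).

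**Precision for a mean such as day 45 FLACC.** Half-width = t(0.975, df) × SD × √(1/n₁ + 1/n₂).

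| Comparison | n | df | √(1/n₁ + 1/n₂) | Half-width |
|---|---|---|---|---|
| Overall, unadjusted | 20 v 10 | 28 | 0.387 | 0.793 SD |
| Overall, adjusted for procedure group | 20 v 10 | 27 | 0.387 | 0.795 SD (within-group SD) |
| Within one procedure group | 10 v 5 | 13 | 0.548 | 1.183 SD |

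The documents give no SD for FLACC, a 0 to 10 score. For an assumed SD of 1, 2 or 3 points, the half-width is about 0.8, 1.6 or 2.4 points overall, and 1.2, 2.4 or 3.5 points within a procedure group. These t-based figures indicate scale. They are not a recommendation to use a t interval on a bounded score.

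**Event rates.** With zero events in n children, the exact (Clopper-Pearson) upper 95% limit is 1 − 0.025^(1/n):
- n = 20: 1 − 0.025^(1/20) = 16.8%
- n = 10: 1 − 0.025^(1/10) = 30.8%

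**Differences in proportions (Newcombe interval).** Two illustrations, with assumed counts:
- 18/20 v 9/10: difference 0, 95% interval about −22 to +31 percentage points.
- 0/20 v 0/10: the Wilson upper limits are 3.84/23.84 = 16.1% and 3.84/13.84 = 27.8%, so the interval is −27.8 to +16.1 percentage points.

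Identical columns therefore leave wide room in both directions.

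**Role of the procedure groups.** At exactly 10:5 in each group, half of each arm is surgical (10/20 and 5/10). Any surgery-laser gap then cancels from the pooled difference. With gap D and within-group SD s, ignoring the groups multiplies the SD by √(1 + D²/(4s²)), which is 1 when D = 0. The documents give neither D nor s.

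If the balance breaks, the gap no longer cancels. Suppose two surgical controls are missing at day 45 (assumption). The control arm is then 3/8 = 0.375 surgical against 0.5 in the insert arm, and the unadjusted difference shifts by 0.125 × D. No dropout allowance is stated.

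**The case against.** The strongest reply is that the protocol is candid: it calls itself a feasibility study and disclaims power, and descriptive reporting fits that. This stands as far as the sample size goes. A reader might infer that 30 children is itself an error, but the documents do not support that, because nothing is claimed about power. Detectable-difference figures would only restate a disclosed limit, so I leave them out. The reply does not cover the missing interval, since low power is a reason to show uncertainty.

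A reader might also infer that the pooled result ignores the randomisation groups and is confounded by procedure. That goes too far. Results are also to be shown by procedure group, and at the planned 10:5 the pooled difference is not confounded. Adjustment gains precision only if surgery and laser differ. It guards against bias only if dropout or uneven filling upsets the balance. Any percentage for lost precision would rest on an assumed gap and SD, and it is nil with no gap. Whether a gap persists to day 45, in children without ocular pain at screening (section 4.1.2), is unknown.

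Finally, no section claims equivalence or non-inferiority. That similar columns might be read that way is a risk in interpretation, not something the plan asserts.

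**Conclusion.** The point holds as a mismatch between objective and analysis. The synopsis objective, primary endpoint and section 2.1 promise a determination or evaluation of efficacy and comparative benefit. Section 8 disclaims the power for it and plans no estimate or interval to put in its place. The size of what goes unshown is about ±0.79 SD overall and ±1.18 SD within a procedure group for a mean, and a true rate of up to 16.8% after zero events in 20. These figures assume two-sided 95% intervals and complete data, and any missing data would widen them. They do not show that the trial is too small for its declared feasibility purpose or that its pooled comparison is biased. The change is worth making and costs little.

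**What to change.** 1. Reword the synopsis objective, the synopsis primary endpoint and section 2.1 as feasibility and estimation, with no superiority or equivalence claim. All three need the change, or the benefit wording survives in one of them.
2. In section 8.1, name the primary estimate: the insert-minus-drops difference in day 45 FLACC with a 95% interval, adjusted for procedure group (surgery or laser). Use a method suited to a bounded, possibly skewed 0 to 10 score, such as a permutation or bootstrap interval stratified by procedure group. If nearly all scores are zero, resampling says little, so also give the proportion above zero by arm. No hypothesis test is needed.
3. Report binary endpoints by arm with exact 95% intervals, and do the same in section 8.1.2 for serious adverse events and events of special interest. Add a risk difference with a score-type interval such as Newcombe. The usual Mantel-Haenszel variance is zero when no events occur, so it would give a zero-width interval where uncertainty matters most.
4. Keep the tables by procedure group as descriptive.

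The cost is a less ambitious stated objective and a few lines of analysis code. Sample size, visits and treatment do not change.
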